Protocol Title: Cognitive Rehabilitation for Gulf War Illness (GWI)
PI: [name]
NCT02161133
War Related Illness and Injury Study Center
Version 8 – 08/02/2018

Background

Gulf War Illness (GWI) is a complex multi-dimensional illness which causes disability. Previous clinical trials (i.e. cognitive behavioral therapy and graded exercise) for GWI have sought to improve disability by increasing activity regardless of symptom presentation. These previous trials for GWI have shown limited efficacy and poor adherence. An innovative treatment approach is to target a specific component of GWI, namely problem-solving ability, known to be associated with disability.

Impairment in problem-solving ability affects Gulf War Veterans (GWV) with GWI and is prospectively related to greater risk of disability. This impairment is also related to poorer adherence to medical regimes, making it difficult for GWVs to manage other aspects of GWI. Problem-solving is considered one of the most complex of cognitive abilities and is related to complicated behaviors such as setting goals, sequencing and multi-tasking. Despite published reports documenting these deficits, there are no treatments that target the problem-solving deficits of GWI in order to reduce disability.

Problem-Solving Therapy

Problem-solving therapy (PST) is a targeted treatment to compensate for the problem-solving deficits of GWI and thereby reducing disability. PST, a top down approach, teaches patients skills to overcome problems like cognitive dysfunction or physical symptoms that impact problem-solving. Compensating for problem-solving deficits would reduce disability and provide information on the effect of treating one component of GWI on other symptoms of GWI.

PST is a treatment approach that teaches patients strategies to address real-life problems. It refers to the process by which people identify and implement effective means to cope with problems encountered in their lives. PST has been developed for individuals with problem-solving deficits. Traditionally, PST for cognitive rehabilitation has been 24 weeks long and is provided in group settings. PST for cognitive rehabilitation is split into two parts: problem-solving orientation phase and problem-solving skill phase and has been delivered over the phone to reduce attrition.

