Participants will be given or mailed a Health Education workbook after the baseline assessment. For participants enrolled at the Bedford VA and Canandaigua VA, the Study Coordinator from the East Orange VA may mail the Health Education workbook. The Health Education workbook will be used in conjunction with the sessions. The content in the Health Education workbook includes didactic information on a variety of health topics pertinent to GWVs, i.e., pain, improving cognition, sleep, diet and physical activity. This information will also be reviewed with the Study Provider during each session. Similar to those randomized to the PST group, at the Study Provider's or PI's discretion, the Health Education protocol may vary in order to meet a Veteran's needs (e.g., changing the order of the information given, having an additional session if feasible).

Participants who are assigned to the health education control condition may be offered the 12-session PST program at the end of the study.

During the sessions, participants will regularly be asked questions on their perception of the sessions, treatment and if they have any new health concerns.

Reducing Attrition

To reduce attrition and the burden on the Veteran, all therapy sessions are done over the phone or video to phone if available. In addition, we plan to make phone calls to remind participants about their scheduled appointments (similar to the VA's automated appointment reminder system). PST has been successfully implemented over the telephone. Prior to starting the treatment, the participant and Study Provider may determine the time that is best for the Veteran (including nights and weekends) and may determine ground rules (for example, not having anyone else in the room, shutting off other telephones to remove distractions). The Study Provider and Veteran may also establish verbal signals to substitute for non-verbal cues, for example, "that's great" or "can I interrupt."

Participants will be allowed to begin or continue with their existing medical regimen throughout the course of the trial and make changes to their existing treatments. Adherence to medical protocols and participation in alternate treatments will be evaluated by a questionnaire at the assessments and this will be controlled for in analyses. The Study Provider may make additional recommendations for additional health care if needed or as appropriate.

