17. *Illness Perception Questionnaire*: The illness perception questionnaire is a well validated and reliable measure of patient's illness cognitions. We have previously used this measure among Gulf War Veterans and found that it predicts adherence and satisfaction with medical care. We will use it to determine if the intervention changes cognitions. The illness perception questionnaire was developed to be modified for different populations and we have modified the questionnaire for use with this population. The Illness Perception Questionnaire has good internal reliability and long term test retest reliability. The IPQ also has good discriminant and predictive validity (Moss-Morris et al., 2002).
18. *Patient Global Impression of Change (PGIC)*: This 2 item scale is widely used in clinical trials to gauge patient satisfaction. The scale asks the patient to rate status change since the beginning of treatment. It has been recommended as a core outcome among patients with medically unexplained symptoms. This will be asked at the follow up time points only (Geisser et al., 2010).
19. *Working Alliance Inventory (WAI) – Self*: The working alliance is one of the most powerful predictors of change in therapy. It assess the participants perception of their relationship with their study provider. The working alliance has excellent reliability (.80) and convergent validity (Munder et al., 2010).
20. *Target Complaints Questionnaire (GOALS)*: The measures ask participants what their current goals for treatment are and then if they meet them. This will enable us to understand the changes and if the treatment worked.
21. *Clients Satisfaction with Treatment*: This short validated measure (8 items) asks about clients' satisfaction with treatment. It is regularly used to assess satisfaction in clinical trials.
22. *MOS – Adherence Scale*: Assesses participants' perceptions of adherence to recommendations. This will assess if participants are following the treatment. The MOS Adherence Scale had adequate reliability and validity (Hays et al., 1995).

After the baseline visit and after the 12th session, participants may be asked about their perceptions of GWI and intervention methods. The qualitative interviews will be up to 45 minutes. This qualitative interview will also allow us to modify the treatment in the future. Qualitative interviews may be conducted on a subset of subjects enrolled over the duration of the project to achieve thematic saturation.

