Data analyses will be conducted both on-site by study investigators and with proper approvals, including DUAs, at our affiliate institutes by current and future study investigators. All analyses will be primarily performed on an intention-to-treat basis. The statistical significance will be defined by a p value < 0.05 , unless specified otherwise. Calculations of the means, standard deviations, proportions, histograms, etc., will be conducted to explore the distributions of the data, identify outliers, and calculate correlations between variables. We will also determine confounders that need to be controlled for in our analyses. We will particularly examine if we need to control for depression measured with the PHQ-8 or PTSD symptoms measured with the PCL based characteristics that exhibit differences at the baseline (pre-intervention).

Due to repeated measures, we will analyze the data using mixed model analysis, with participants nested within therapists modeled by random effects. To address H1, disability (WHODAS II scores) will be treated as the dependent variable, and treatment assignment [PST vs. Health education], time [pre- vs. post-intervention] and their interaction will be modeled as fixed effects. Differences in the improvement of disability between Problem-solving therapy and Health education will be evaluated by the treatment by time interaction. Linear contrasts will be constructed to evaluate the improvement in disability for each treatment separately. Variables such as age, gender, education and the confounders identified in the preliminary analysis will be controlled as covariates in the statistical analyses. Data transformations (e.g., square root, log,

etc.) will be used to normalize data where necessary. The same mixed model analysis strategy will be applied to address H2a, H2b, H3a and H3b. We will also explore, using this same mixed model strategy, the impact of PST therapy on each of the four individual neuropsychological tests scored as a composite and scored individually (Category Test, CPT 3, Stroop Test, and TMT). We will use the same data analysis strategy to examine all secondary outcomes. These will be reported as secondary outcomes and will primarily be used to generate hypotheses.

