	MOS Adherence Scale [MOS-Adhere]	5		X		X	
	Patient Global Impression of Change [PGIC]	2				X	X
	Client Satisfaction Scale [Client Sat]	8				X	
Estimated Completion Time for Treatment Perceptions Domain: 8 minutes							
Veterans Perceptions of Gulf Illness Perceptions Questionnaire [IPQ]			60	X		X	
Estimated Completion Time for Perceptions Domain: 10 minutes							
Total Estimated Completion for Questionnaires			35-45 mintue	70 minutes	20 mintues	70 minutes	35 minutes
Problem-Solving Neuropsychological Assessments	Halstead Category Test Short Form: Russell Revised Short Version [RCat]			X		X	
	Stroop Test			X		X	
	Trail Making Test Part A & B [TMT]			X		X	
	Continuous Performance Task [CPT-III]			X		X	
	Rey-15			X		X	
Estimated Completion Time for Neuropsychological Assessments: 50 minutes							
Qualitative Interviews				X (After Baseline is completed)		X (After Follow up is completed)	
Estimated Completion Time for a Qualitative Interview: 45 minutes

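### The plan promises to control for adherence and other treatments without limiting this to baseline values; if follow-up values enter the H1 model, the contrast may no longer estimate the effect of assignment

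*Combined protocol and SAP*

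**What the plan says.** The commitment stands in the Reducing Attrition paragraph on concurrent care, not in the analysis section. That paragraph first says "Participants will be allowed to begin or continue with their existing medical regimen throughout the course of the trial" and that they may alter treatments they already have. It then says, of adherence to medical protocols as well as other care: "participation in alternate treatments will be evaluated by a questionnaire at the assessments and this will be controlled for in analyses". The next sentence adds: "The Study Provider may make additional recommendations for additional health care if needed or as appropriate".

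The questionnaire is not named. Two instruments in the Summary List of Measures and Timeline are likely candidates. The MOS Adherence Scale (5 items) is marked at two points, read as baseline and 12 weeks. Healthcare Access (17 items) is marked at baseline, 12 and 24 weeks. Of the adherence scale, the questionnaire list says: "This will assess if participants are following the treatment".

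The Background says of impaired problem-solving: "This impairment is also related to poorer adherence to medical regimes, making it difficult for GWVs to manage other aspects of GWI".

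Data Analysis, part a, tests H1 by the treatment-by-time interaction in a mixed model of WHO-DAS scores. Its covariate list is open: age, gender and education are given as examples, together with confounders found in preliminary analyses. The confounders it singles out, depression and PTSD symptoms, are judged on baseline differences. Adherence and other treatments are not mentioned. The section also states: "All analyses will be primarily performed on an intention-to-treat basis".

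**The concern.** A covariate measured after randomisation can be a consequence of the assigned arm. Adherence is a plausible case here. The protocol associates the deficit that PST targets with poorer adherence, and says this makes other aspects of the illness harder to manage. If PST improves adherence and adherence reduces disability, that improvement is part of the effect of PST. Holding adherence fixed removes it.

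There is a second mechanism. An unmeasured factor, such as underlying health or motivation, may drive both use of other care and disability. If PST also changes use of other care, conditioning on it links arm to that factor and can produce a difference where none exists.

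A baseline-only reading of the clause is possible but not natural. The sentence directly follows permission to change treatment during the trial, and baseline values cannot capture such changes. The description of the adherence scale adds a further difficulty: if it reflects following of the study sessions, adjusting for it conditions on uptake of the randomised treatment.

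What is at stake is the meaning of the primary contrast. It would become something other than the effect of assignment, without the protection of randomisation, and the direction of any bias could not be known in advance.

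**Working it through.** The plan gives no figure to reproduce: no effect size, SD, power or allocation ratio, only a sample of up to 300. Everything below is therefore illustrative. Assumptions: 150 per arm, two-sided 0.05, SD units, improvement coded positive, total PST effect 0.35 SD. Let a be the effect of PST on the covariate, b the effect of the covariate on disability, and r a covariate–outcome correlation due only to an unmeasured shared cause.

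**1. Real effect removed (time-varying covariate).** Total effect = direct effect + a × b; adjustment leaves the direct part.
- a = b = 0.3: removed 0.3 × 0.3 = 0.09 SD. Remaining 0.35 − 0.09 = 0.26 SD. Share 0.09 / 0.35 = 26%.
- a from 0.1 to 0.5 and b from 0.1 to 0.4: removed 0.1 × 0.1 = 0.01 SD (3%) to 0.5 × 0.4 = 0.20 SD (57%).
- Power before adjustment: √(2/150) = 0.1155; 0.35 / 0.1155 = 3.03; Φ(3.03 − 1.96) = 86%.
- Power after adjustment at a = b = 0.3: SD = √(1 − 0.09) × √(1 + 0.09/4) = 0.965; 0.26 / (0.965 × 0.1155) = 2.33; Φ(2.33 − 1.96) = 65%. Over the whole grid, adjusted power runs from 84% down to 28%.

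**2. Simulation of the same case.** 1,000 complete pre/post trials, analysed as change scores.

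| Analysis | Estimate (SD) | Power |
|---|---|---|
| No adjustment | 0.35 | 82% |
| Change in the covariate | 0.26 | 61% |
| Baseline value only | 0.35 | 83% |

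Power is a little below the formula because the simulated change score has variance 1 + 0.3² = 1.09 rather than 1.

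**3. False effect under a true null.** The shift is −a × r.
- a from 0.1 to 0.5 and r from 0.1 to 0.4: size 0.01 to 0.20 SD; type I error 5.1% to 45%.
- Simulation with a = 0.5 and shared-cause loadings of 0.5 on both covariate and outcome: within-arm slope 0.5 × 0.5 / 1 = 0.25, so the shift is −0.5 × 0.25 = −0.125 SD. Simulated: −0.13 SD and type I error 15.9%, against 5.2% unadjusted and 5.5% with baseline-only adjustment.
- The sign reverses if a and r have opposite signs. With a = 0 the shift is zero.
- The −0.13 comes from a change-score analysis. A random-intercept model weights a time-varying covariate differently, so the figure shows the mechanism and does not predict the planned model.

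**4. How the covariate enters matters.** In complete two-time data, the treatment-by-time contrast is the difference between arms in mean change.
- Time-constant main effect (for example, the week-12 value entered once): it contributes equally before and after treatment and cancels from the change. Loss 0; in simulation the interaction was 0.35 with and without it.
- Time-varying: loss a × b = 0.09 SD.
- Week-12 value interacted with time: the change depends on b × (week-12 value − baseline value). With equal variances and baseline-to-week-12 correlation ρ, the slope on the week-12 value is b × (1 − ρ), so the loss is a × b × (1 − ρ). For ρ = 0.5 this is 0.09 × 0.5 = 0.045 SD; for ρ = 0.6 it is 0.09 × 0.4 = 0.036 SD.

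The plan does not say which form it intends.

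**The case against.** The strongest reply is that the clause commits to less than it seems to. It names no model, time point, instrument or form of entry, and it sits in a section about attrition. The assessments include baseline. The Data Analysis section, which does define the H1 model, does not name these covariates, and its example of confounder selection uses baseline differences. All this is correct, so the point cannot be put as a statement that H1 is definitely adjusted for follow-up values. The clause is nevertheless unqualified, and the open covariate list in Data Analysis does not cancel it.

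Four further objections stand and limit the claim:
- A reader might infer that the protocol says poor problem-solving causes poor adherence. The Background reports an association only. It makes the route plausible, not established.
- A reader might infer that provider recommendations change other care differently by arm. Providers may make them to participants in both arms, and nothing in the documents shows a difference.
- A reader might infer that the adjustment contradicts intention to treat. It moves nobody between arms, so there is no strict contradiction. The difficulty is that the adjusted contrast answers a different question.
- The 0.09 SD loss is not a property of the planned test as written. It requires time-varying entry and vanishes in complete pre/post data for a time-constant main effect. With missing follow-up, that cancellation need not be exact.

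**Conclusion.** The concern holds in a conditional form. The protocol commits to adjusting for adherence and other treatments without limiting the adjustment to baseline. On the natural reading, values that PST could change may enter the H1 model. Entered as time-varying covariates or interacted with time, they may bias the treatment-by-time contrast in either direction.

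The size cannot be determined from the documents. The central illustration, 0.09 of 0.35 SD, rests on assumed paths of 0.3 and 0.3; the assumed grid spans 3% to 57% of the effect. Bias is absent if the arms do not differ on the covariate. The documents do not support saying that the planned H1 test is biased, or by a given amount. They do support saying that the rule as written permits it and that the two sections must be reconciled before analysis.

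**What to change.** Amend the Reducing Attrition clause and align Data Analysis, part a, for example: *Only values of adherence and concomitant treatment recorded before randomisation may be covariates in the H1, H2a, H2b, H3a and H3b models. Values recorded after randomisation will be summarised by arm and used only in analyses labelled exploratory, sensitivity or mediation, with their assumptions stated. The H1 contrast estimates the effect of assignment to PST versus health education, whatever other treatment is received.*

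The amended clause should also name the questionnaire it refers to. The existing provision for mediation and exploratory analyses can accommodate the follow-up values, so nothing planned is lost. The cost is a few sentences in two places, with no new data and no change to the assessment schedule.
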